9.6. Data Management

All de-identified (pseudonymized in Nordic countries), inpatient, outpatient and other healthcare-transactional data for patients with at least one prescription of Mysimba/Contrave will be obtained and maintained on a server by an analyst experienced in evaluating that database (patient level data will remain within each country). The data will be stored and accessed according to the sites' data privacy and security practices.

Data management and transformation to analytic datasets from the line-level data will be performed by an experienced analyst. Data extraction, curation of analytic data sets, analysis, and generation of tables and figures will be conducted in accordance with established standard operating procedures at each organization conducting data analysis. Additionally, code will be reviewed by another analyst (or the project director) adept in the coding language and analysis of the data. Face validity of descriptive statistics and incidence rates will be reviewed by the research team.

Management of the US data source will be conducted in accordance with the internal quality management system of the organization conducting the analysis, including integrated Standard Operating Procedures (SOPs) for conducting non-interventional PASS studies with secondary data. Manipulation, housing, and analysis of the US data source will occur within a managed virtual private cloud using native (i.e., secure) Amazon Web Services offerings, including a Postgres(-like) database. Statistical analyses will be conducted, principally, using SAS 9.4. If

necessary, packages from R, Python, or SPSS will be utilized – and such use will be described in the report. No individual data will be downloadable from this cloud environment. For access to the Scandinavian national patient registries, researchers or a vendor located in Scandinavia are required to access data from the registries on secure servers of registry owners.

Applications for data access to the Scandinavian registries in each of the four countries will be pursued once EC approval of the NB-451 protocol is granted in each of the Nordic countries. Aggregated data (output of data analyses) will be saved and stored on secure servers and analyzed using secure systems. Among other things, all employees of the vendor will have a password for the IT system. All work-related material must be saved on a network drive, which is scanned to prevent misuse, and backup happens automatically. Rules also apply to e-mail accounts, PCs and mobile devices.

Any research partner in Nordic countries that applies for access to the Scandinavian patient registries will work according to their legal frameworks and their institutional IT policies.

9.7. Data Analysis

9.7.1. Timing of Feasibility, Interim, and Final Analyses

Prior to study start, feasibility was conducted annually.

One cohort per country will be extracted each time the database is opened. Per database, the following analyses will be conducted:

- 1. ongoing data review, for each of the participating Nordic countries
- 2. a first (interim) analysis when a database size reaches 750 patients with up to 548 days of activity in database after index date
- 3. a second (interim) analysis when an additional 2,250 patients (total 3,000 patients) with a Mysimba/Contrave index date are included in a database with up to 548 days of calendar time available in the database after the index date
- 4. a final analysis of the database will be conducted for the final report including all patients from the EU data sources meeting the inclusion criteria for the study as of 15 February 2025. If >3000 patients are available at the time of an interim analysis, the final report for

that database will be submitted one year after data is accessible. If final data is available 31 Dec 2024, the final report will be submitted by 31 Dec 2025.

All analyses will be performed separately in each country. All patients in the study will be included in the analysis, regardless of whether there is evidence of any contact with the health system (as registered by any data in the database) after inclusion into the study. One interim and one final analysis will be conducted per country. A final report will be generated when the last database in the study conducts the final analysis (when the last database has >3000 Mysimba patients, or 31 Dec 2025, whichever comes first). The final analysis from the four participating Nordic countries will be included in that report which will be accompanied by synthesis of findings, discussion, and interpretation across all Nordic databases.

9.7.2. Descriptive Statistics

For demographic and baseline variables and duration of Mysimba/Contrave use (measured as both continuous treatment of the initial Mysimba/Contrave duration and the total treatment duration of Mysimba/Contrave), descriptive statistics will be used to describe continuous variables, (e.g., mean, standard deviation, median, quartiles 1 and 3, minimum, maximum, and two-sided 95% confidence intervals [CI]). Categorical variables will be described by the total and percentage of each response and the number of missing data (data that are unavailable in the database).

Patterns of Mysimba/Contrave use will be described by mean (standard deviation, SD) and median (quartile1, quartile 3) number of prescriptions per patient, number and duration of treatment episodes per patient as well as the average duration between prescription episodes. Analyses will be performed for all users of Mysimba/Contrave, including an assessment of whether the subjects have adhered to the prescribed treatment with Mysimba/Contrave according to the terms of the SmPC (adapted to the local country SmPC for the data source as needed, and adapted if BMI is not accessible). The number and proportion of patients who received treatment with Mysimba/Contrave will be provided according to the following subgroups (availability of variables to be summarized in SAP):

(a) Inconsistent with labelled indication:

- 1) Age < 18 years
- 2) Use other than management of weight
- 3) Management of weight in a patient who does not have obesity or is not overweight and has a weight-related comorbidity
- 4) A prescribed maintenance dose other than the Mysimba/Contrave 32mg/360mg
- 5) Continued use past 16 weeks without \geq 5% weight loss
 - (b) Incompatible with the stated contraindications set out in the SmPC:
- 1) A current diagnosis of uncontrolled hypertension, seizure disorder (or history of seizures), or end-stage renal failure
- 2) A history bipolar disorder, anorexia nervosa or bulimia
- 3) A current dependence on chronic opioids or opiate agonists (e.g., methadone)
- 4) A current state of acute opiate withdrawal
- 5) Any concomitant treatment containing bupropion, naltrexone, or a MAOI
- 6) Patients with a known central nervous system tumour
- 7) Patients undergoing acute alcohol or benzodiazepine withdrawal
- 8) Patients with severe hepatic impairment

The proportion of users non-adherent to each component of the indication/contraindications will also be determined. Small numbers will be presented as "<x" where "x" represents the defined threshold for the smallest number of patients that is allowed to be presented from the data source. Since information on the titration scheme is expected to be sparse (and, not present in the Nordic data), a sensitivity analysis will also be conducted where the first dispensing (112 tablets) is allowed to cover the full time of titration (i.e., 7 tablets in first week (n=7 days), 14 tablets in second week, 21 tablets in third week, and the remaining 70 tablets over 17.5 days (4 tablets per day) for a total of 38.5 days). The possible gap will be 19 days (half of the days' supply) before the second dispensing. Duration of Mysimba/Contrave use and adherence will be recalculated based on this adjustment. Adherence to the titration scheme will be confirmed for a patient if the second dispensing occurs within 40 days +/- 7 days from the first dispensing. Additionally, another sensitivity analysis will be implemented in which patients with evidence of renal or liver impairment are allowed up to 56 days for consumption of *each* dispensing to account for

continued use and adherence within these patients who are unlikely to reach the full recommended dosage due to renal or hepatic dosage adjustments.

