3. DRUG DESCRIPTION

Generic Name: naltrexone hydrochloride and bupropion hydrochloride extended-release tablet

Trade Name: MYSIMBA®/Contrave®

Indications for Use:

Mysimba/Contrave is indicated as an adjunct to a reduced-calorie diet and increased physical activity for chronic weight management in adults with an initial body mass index (BMI) of:

1. 30 kg/m² or greater (obese) or

2. 27 kg/m² or greater (overweight) in the presence of at least one weight-related comorbidity (e.g., hypertension, type 2 diabetes mellitus, or dyslipidemia).

Limitations of Use:

- 1. The effect of Mysimba/Contrave on cardiovascular morbidity and mortality has not been established.
- 2. The safety and effectiveness of Mysimba/Contrave in combination with other products intended for weight loss, including prescription drugs, over-the-counter drugs, and herbal preparations, have not been established.

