7. RATIONALE AND BACKGROUND

According to the World Health Organisation, weight-related health issues are some of the most significant global public health challenges. Worldwide obesity has nearly tripled since 1975. Obesity (body mass index [BMI] ≥30 kg/m2) and being overweight (BMI ≥27 kg/m2 to <30 kg/m2) are linked to psychosocial conditions and are major risk factors for chronic diseases, including cardiovascular disease, orthopaedic/degenerative joint disease, and diabetes. Globally there are more people who are obese than underweight and this occurs in every region except parts of sub-Saharan Africa and Asia. The World Health Organisation estimates that the prevalence of obesity and overweight, among adult men and women in Europe, is over 20% and over 50%, respectively. The major health risks and complications associated with obesity negatively affect quality of life and reduce average life expectancy. In addition to burdening the health care system, the treatment of overweight and obesity is a public health imperative. Long-term lifestyle changes are essential to mitigate obesity-related morbidity and mortality; however, for overweight and obese individual's lifestyle changes alone are insufficient, and pharmacotherapy should be considered and added.

Mysimba/Contrave, a fixed-dose combination of naltrexone (an opioid receptor antagonist) and bupropion (a selective neuronal re-uptake inhibitor of noradrenaline and dopamine), was approved in Europe for the treatment of adults with a BMI of \geq 30 kg/m2 (obese) or \geq 27 kg/m2 to <30 kg/m2 (overweight) in the presence of one or more weight-related co-morbidities (e.g., type 2 diabetes, dyslipidaemia, or controlled hypertension).

The European Medicines Agency (EMA) requested that Orexigen Therapeutics Ireland Limited (Orexigen) provide additional information on the utilisation of Mysimba in Europe and further

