8. RESEARCH QUESTIONS AND OBJECTIVES

The aim of the study is to assess the long-term (548 days) real-world utilization patterns of Mysimba/Contrave use among patients who are prescribed Mysimba/Contrave. There are no a priori hypotheses for this study.

The primary objectives of the study are:

- To describe demographic and baseline characteristics of patients initiating use of Mysimba/Contrave; and
- 2. To evaluate patterns of Mysimba/Contrave initiation and use, including number of prescriptions, number of treatment episodes and duration between prescriptions, as well as estimating the number and percentage of patients compliant and non-compliant with the SmPC.

Analysis of compliance to the labelled indication and contraindications will be adapted to the specific SmPC for the country relevant to the data source (s). Examples of non-compliance include, but are not limited to:

Use inconsistent with labelled indication:

- 1. Age <18 years
- 2. Use other than management of weight
- 3. Management of weight in a patient who does not have obesity or is not overweight and has a weight-related comorbidity
- 4. A prescribed maintenance dose other than the Mysimba/Contrave 32mg/360mg
- 5. Continued use past 16 weeks without \geq 5% weight loss

Use in patients with contraindications:

- 6. A current diagnosis of uncontrolled hypertension, seizure disorder (or history of seizures), or end-stage renal failure
- 7. A history of bipolar disorder, anorexia nervosa or bulimia
- 8. A current dependence on chronic opioids or opiate agonists (e.g., methadone)
- 9. A current state of acute opiate withdrawal
- 10. Any concomitant treatment containing bupropion, naltrexone, or a MAOI
- 11. Patients with a known central nervous system tumour

Proprietary and Confidential:

- 12. Patients undergoing acute alcohol or benzodiazepine withdrawal
- 13. Patients with severe hepatic impairment (dependent on local SmPC)

The secondary objectives of this study are:

- 1. To assess and compare the observed incidence of AESIs in usual clinical practice among users of Mysimba/Contrave compliant and non-compliant with the SmPC. AESIs include new onset of the following:
 - 1. Seizures
 - 2. Suicidality (i.e., suicidal ideation, attempted suicide or completed suicide)
 - 3. Neuropsychiatric events (i.e., mania or depression)
 - 4. Hepatotoxicity
 - 5. Severe hypersensitivity reaction
 - 6. Serotonin syndrome

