- 6. Serotonin syndrome
- 7. Major adverse cardiovascular events (i.e., cardiovascular-related death, non-fatal myocardial infarction, or non-fatal stroke)

Deaths will also be described by treatment group, for those with vital status available.

- 7. Treatment discontinuation (assessed using ATC [outpatient, Nordic data] or NDC [US data])
- 8. Reason(s) for treatment discontinuation (obtained via ICD-10 codes in the 90 days prior to discontinuation)

All variables will be identified from the data sources via a pre-specified list of definitions (i.e., code lists; see Appendix 2). Occurrence of AESI based on diagnostic codes will be summarized for all patients, and for a subgroup of patients who do not adhere to conditions of the EU SmPC for the Scandinavian countries (adapted to local SmPC as needed) or to the FDA SmPC for the US. Such criteria include: not meeting appropriate criteria for the indication [obese (BMI \geq 30 kg/m²), or being overweight (BMI \geq 27 kg/m² to < 30 kg/m²) and having at least one weight-related co-morbidity (e.g., type 2 diabetes, controlled hypertension, or dyslipidemia) based on diagnostic codes. If BMI is not available, diagnostic and procedure codes for obesity and weight loss will be applied, recognizing that it will likely produce a more obese population than would be identified by BMI. Subgroup analyses will also be conducted to assess continuous treatment in patients with either renal or hepatic impairment.

Initiation of specific medications that could result with the occurrence of an event corresponding to an AESI (e.g., newly initiating anti-epileptic/seizure medication, newly initiating medications indicated for mania or depression) will also be tabulated. For hepatotoxicity, liver function tests can be used (when available) in addition to diagnostic codes.

For reason(s) patients who discontinue treatment (i.e., do not refill their prescription), events (potential AESIs and contraindications) and clinical status (magnitude of weight loss or gain)

Proprietary and Confidential:

occurring within the 90-day window prior to discontinuation will be summarized. It should be noted that weight may not be available in the Scandinavian registries.

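### The off-label BMI item in sections 8 and 9.7.2 negates the indication wrongly and, taken literally, counts some on-label patients as non-compliant

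*Protocol*

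**What the plan says.** Section 3 gives the labelled indication in two arms: "30 kg/m² or greater (obese) or" "27 kg/m² or greater (overweight) in the presence of at least one weight-related comorbidity". Section 7 repeats it but closes the second arm at the top, with "being overweight (BMI ≥27 kg/m2 to <30 kg/m2". Section 9.3.2 uses the same closed band.

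Section 8 makes "estimating the number and percentage of patients compliant and non-compliant with the SmPC" part of primary objective 2. Among its examples of use outside the indication, item 3 reads "Management of weight in a patient who does not have obesity or is not overweight and has a weight-related comorbidity". Section 9.7.2 repeats that sentence as subgroup (a) 3 and adds: "The proportion of users non-adherent to each component of the indication/contraindications will also be determined". The compliance assessment there is to be "adapted to the local country SmPC for the data source as needed, and adapted if BMI is not accessible".

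Section 9.3.2 describes the non-adherent subgroup for the AESI summary differently. It speaks of "not meeting appropriate criteria for the indication" and then sets out the whole indication (obese, or overweight with at least one comorbidity). Section 9.7.3.1 takes its compliant and non-compliant groups from a list that it places in section 9.7.1. That section covers the timing of analyses and contains no such list; the list stands in 9.7.2.

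**The concern.** The indication has the form *A or (B and C)*. Its negation is *not A, and not (B and C)*. The sentence in sections 8 and 9.7.2 negates A and B one at a time, keeps the 'or' between them, and leaves the comorbidity un-negated. Having a comorbidity, which helps to qualify an overweight patient under the label, therefore becomes part of the condition for being off-label.

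This is an operational definition with its own reported proportion. It also contributes to the primary compliance percentage and, through the list that section 9.7.3.1 appears to intend, to the groups in which AESI incidence is compared. Section 9.7.1 has each country analysed separately, and section 9.6 leaves the work to analysts under their own organisations' procedures. Different readings in different databases would make the percentages non-comparable in the planned synthesis.

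**Working it through.** **Inputs.** O = obese (BMI ≥30). W = overweight, either 27 to <30 (sections 7 and 9.3.2) or ≥27 with no upper bound (section 3). C = at least one weight-related comorbidity. On-label = O or (W and C). Off-label = not O and not (W and C). The protocol states no expected percentage for this item, so there is no figure to reproduce.

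**Logic check.** Four readings of the sentence are set against the label:

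- R1, literal: (not O) or (not W and C)
- R2, 'or' grouped first: (not O or not W) and C
- R3, 'or' taken as 'nor', comorbidity left un-negated: (neither O nor W) and C
- R4, 'or' taken as 'nor', second 'not' covering both overweight and comorbidity: not O and not (W and C)

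| Patient | Label | R1, W = 27 to <30 | R1, W = ≥27 | R2, W = 27 to <30 | R3 | R4 |
|---|---|---|---|---|---|---|
| <27, no C | off | flagged | flagged | **missed** | **missed** | flagged |
| <27, C | off | flagged | flagged | flagged | flagged | flagged |
| 27 to <30, no C | off | flagged | flagged | **missed** | **missed** | flagged |
| 27 to <30, C | on | **flagged** | **flagged** | **flagged** | – | – |
| ≥30, no C | on | – | – | – | – | – |
| ≥30, C | on | **flagged** | – | **flagged** | – | – |

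Bold marks an error. R1 flags on-label patients under either definition of overweight. R2 does so too and also misses off-label patients without a comorbidity. R3 flags no on-label patient but misses the same off-label patients. Only R4 matches the label. It is the rule that section 9.3.2 states.

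**Size, illustrative only.** The documents give no BMI or comorbidity distribution. Assume BMI is normal with mean/SD between 37/6 and 32/4, and C is present in 40–60%, independently of BMI. Let a, b and o be the shares with BMI <27, 27 to <30 and ≥30, and c the comorbidity share.

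- Mean/SD 37/6: a = 4.8%, b = 7.4%, o = 87.8%
- Mean/SD 32/4: a = 10.6%, b = 20.3%, o = 69.1%

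Share of on-label patients flagged under R1:

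- W = ≥27: bc / (o + bc)
- W = 27 to <30: (bc + oc) / (o + bc)

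Low end (37/6, c = 0.4): bc = 2.96 and o + bc = 90.76.

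- W = ≥27: 2.96/90.76 = 3.3%
- W = 27 to <30: (2.96 + 35.12)/90.76 = 42.0%

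High end (32/4, c = 0.6): bc = 12.18 and o + bc = 81.28.

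- W = ≥27: 12.18/81.28 = 15.0%
- W = 27 to <30: (12.18 + 41.46)/81.28 = 66.0%

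Effect on the item's own proportion over the same range of assumptions:

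- Correct rule, a + b(1 − c): about 8–23%
- R1 with W = ≥27, a + b: about 12–31%
- R1 with W = 27 to <30, a + b + oc: about 47–72%

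**The case against.** The case against is substantial. The protocol already contains the right rule: sections 3 and 7 state the indication, and section 9.3.2 negates it as a whole. Section 8 introduces its list as examples, and section 9.7.2 asks for assessment according to the terms of the SmPC. An analyst who goes to the label will not count BMI 36 with type 2 diabetes as off-label. Reading 'or' as 'nor', with the second 'not' covering the whole phrase (R4), recovers the label rule, so a reader who infers that no reading of the sentence works would be wrong. A reader might also list section 9.3.2 as another place with the same fault; it is the correct statement and the best evidence of intent.

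Reach is limited as well. Appendix 3 lists BMI as partial for the US and shows no availability for the four Nordic sources, where codes or predicted BMI would stand in.

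All of this stands and limits the weight of the point, but it does not remove it. The literal sentence still flags a patient whom the label includes, under either definition of overweight, and it appears in both sections that govern the primary percentage. The adaptation clause covers local labels and missing BMI, not and/or logic, and the code-based fallback in section 9.3.2 does not restate the grouping. The sentence is a rule stated wrongly, not a detail left to the SAP.

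**Conclusion.** The point holds as a drafting error that contradicts the protocol's own indication. If the wording in sections 8 and 9.7.2 is followed literally, on-label patients with BMI 27 to <30 and a comorbidity are counted as non-compliant. So are obese patients with a comorbidity where overweight means 27 to <30. The direction depends on the reading: the literal one inflates non-compliance, while R3 understates it.

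The documents do not show that the reported percentage will be wrong. That depends on whether analysts follow this sentence or section 9.3.2, and the SAP is not at hand. Nor do they support any single figure for the error. The 3–15% and 42–66% of on-label patients rest wholly on the assumed BMI and comorbidity distributions, and the higher range also needs the closed band of sections 7 and 9.3.2 rather than the open one of section 3. The practical exposure is mainly in the part of the US data with BMI recorded. Section 9.4.2 anticipates more than 20,000 eligible US users.

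**What to change.** Reword item 3 of section 8 and (a) 3 of section 9.7.2 to match section 9.3.2, for example: *Management of weight in a patient who has neither (i) obesity nor (ii) overweight together with at least one weight-related comorbidity, as defined in the local SmPC.* This keeps the restriction to weight management, so the item stays distinct from item 2, and it leaves the thresholds to the label.

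State that the same and/or grouping applies to the code-based definition where BMI is unavailable. Have section 9.7.3.1 refer to the list in section 9.7.2 instead of 9.7.1. Section 9.3.2 needs no change.

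The cost is one sentence in two places, one clarifying line, one corrected cross-reference and a check of the derivation code. No data collection changes.

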 - 7. Major adverse cardiovascular events (i.e., cardiovascular-related death, non-fatal myocardial infarction, or non-fatal stroke)

Deaths will also be reported in patients in which vital status is known.

- 2. To assess the proportions of patients in the following groups who are at increased risk for AESI and to describe the characteristics of the patients with AESI in these groups:
 - 1. Any user of Mysimba/Contrave
 - 2. Users compliant with SmPC
 - 3. Users out of compliance with SmPC, as described above
- 3. To assess the duration of Mysimba/Contrave use
- 4. To identify to the extent possible within the data sources:
 - 1. Initial titration scheme and proportion aligned with SmPC
 - 2. Dose adjustment in special populations and proportion aligned with SmPC
 - 3. Reasons for treatment discontinuation (not typically available in these databases)
 - 4. AESIs leading to treatment discontinuation (not typically available in these databases)

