9.3.1.2. Dosage of Mysimba/Contrave Use

When available, the listed dose of Mysimba/Contrave within each prescription or dispensing will be used as the dose for that patient. However, dose is unlikely to be available in Nordic data and sporadically available in US data. When dose is not provided, then an assumption of the standard dosing (4 pills per day with 32mg naltrexone and 90 mg bupropion in each pill) will be used as the dose for primary analyses. Sensitivity analyses will assign alternate dosing for specific patient groups (see section 9.7.2).

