9.7.3.1. Incidence Rates of AESIs in Subgroups of Patients

If data are available and appropriate predictors are available in the respective database, sensitivity analyses around the definition of each type of AESI will be performed. Incidence proportion and density of each type of AESI will also be calculated for the subgroup of patients compliant or non-compliant with the EU SmPC (as listed in section 9.7.1, the criteria will be adapted for the relevant country of the data source stems if the SmPC differ across such countries, i.e., for U.S.), including relevant comorbidities, concomitant medications, and pregnancy. Adaptations will be made if BMI is not available; these will be described in the SAP. The incidence rate (and 95% CI) of new onset comorbidities and concomitant medication after initiation of Mysimba/Contrave will be assessed. Incidence rates will be determined both for the person-years of time exposed to Mysimba/Contrave (i.e., while patient taking medication) after the index date as well as for all person time through 548 days after the index Mysimba/Contrave prescription.

The incidence rate (and 95% CI) of pregnancy and breastfeeding after the Mysimba/Contrave index date will be assessed among females initiating Mysimba/Contrave. These analyses will be conducted in data sources where the necessary variables are present.

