9.7.4. Titration, Change in Dose, and Discontinuation

Among patients with available information, the proportion of patients with titration and dosing changes in alignment with the EU SmPC will be calculated. The local SmPC for the country of the data source may be used, if different than the EU SmPC.

Because reason discontinuation is rarely found in real world data, clinical events of interest and health status occurring within the 90-day window prior to discontinuation will be summarized for patients who discontinue treatment (i.e., do not refill their prescription). However, attribution to product is not possible.

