Appendix 3. Variable Availability by Country (final list to be confirmed in SAP)

LEGEND: "--" indicates that the information is not available

Partial = may be available for some patients

Limited = anticipated to be underreported

Yes = likely to be available if true for patient

Unlikely = available for some patients; may not be accurate

Calculated = assumptions can be used to derive a variable for this information

Variable	US	Denmark	Norway	Sweden	Finland
Mysimba prescription	Yes				
Date of Mysimba	Yes				
prescription					
Mysimba dispensing	Partial	Yes	Yes	Yes	Yes
Date of Mysimba	Partial	Yes	Yes	Yes	Yes
dispensing					
Mysimba dosage for each	Partial				
dispensing					
Initial titration scheme	Maybe				
Dosing of Mysimba during	Maybe				
titration					
Dose adjustment of	Partial				
Mysimba (e.g., for special					
population)					
Maintenance dose of	Maybe				
Mysimba					
Mysimba days' supply	Calculated	Calculated	Calculated	Calculated	Calculated
Date of	Partial	Yes	Yes	Yes	Yes
eligibility/enrolment					
available to identify					
continued					
engagement/recording of					
clinic visits					
Age	Yes	Yes	Yes	Yes	Yes
Sex	Yes	Yes	Yes	Yes	Yes
BMI	Partial				
Height	Partial				
Weight	Partial				
Diabetes	Yes	Yes	Yes	Yes	Yes
Dyslipidaemia	Yes	Yes	Yes	Yes	Yes

Proprietary and Confidential:

This document cannot be used, distributed, or reproduced in any way without the prior written consent of Currax Pharmaceuticals LLC.

Anorexia nervosa	Yes	Yes	Yes	Yes	Yes
Bulimia	Yes	Yes	Yes	Yes	Yes
Hypertension	Yes	Yes	Yes	Yes	Yes
Uncontrolled hypertension	Yes	Yes	Yes	Yes	Yes
Moderate or severe renal	Yes	Yes	Yes	Yes	Yes
impairment	1 68	1 68	1 68	1 68	1 68
End-stage renal disease	Yes	Yes	Yes	Yes	Yes
Seizure	Yes	Yes	Yes	Yes	Yes
Seizure disorder	Maybe	Unlikely	Unlikely	Unlikely	Unlikely
Hepatic impairment via	Maybe				
Child-Pugh score	Mayoc				
Hepatic impairment via diagnosis	Yes	Yes	Yes	Yes	Yes
Central nervous system	Yes	Yes	Yes	Yes	Yes
tumour					
Substance use/abuse	Limited	Limited	Limited	Limited	Limited
Acute opiate withdrawal	Limited				
Acute alcohol or	Limited				
benzodiazepine withdrawal					
Suicidality	Limited	Limited	Limited	Limited	Limited
Mania	Limited	Limited	Limited	Limited	Limited
Bipolar disorder	Limited	Limited	Limited	Limited	Limited
Major depressive disorder	Yes	Yes	Yes	Yes	Yes
Hepatotoxicity	Yes	Yes	Yes	Yes	Yes
Severe hypersensitivity reaction	Limited	Limited	Limited	Limited	Limited

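### Criterion (a)4, read literally, counts a recorded dose reduction that follows the label as non-compliant, while other parts of the protocol count it as aligned (minor; US data only)

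*Protocol*

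**What the plan says.** Protocol section 9.7.2, list (a) item 4, repeated as item 4 of the non-compliance list in section 8, classes as inconsistent with the labelled indication "A prescribed maintenance dose other than the Mysimba/Contrave 32mg/360mg". Neither place attaches a qualifier to the item.

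Three other statements treat a lower dose as possibly correct:

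- Section 8, secondary objectives: "Dose adjustment in special populations and proportion aligned with SmPC".
- Section 9.7.4: among patients with the information, "the proportion of patients with titration and dosing changes in alignment with the EU SmPC will be calculated", with the local SmPC as an alternative where it differs.
- Section 9.7.2, on the 56-day sensitivity analysis: patients with renal or liver impairment are "unlikely to reach the full recommended dosage due to renal or hepatic dosage adjustments".

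The compliance split is used twice. It yields the number and percentage non-compliant under primary objective 2. It also defines the AESI subgroups in section 9.7.3.1, where incidence is calculated "for the subgroup of patients compliant or non-compliant with the EU SmPC", with adaptation for the US. Section 9.3.2 judges adherence against the EU SmPC in the Nordic countries "or to the FDA SmPC for the US".

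On data, section 9.3.1.2 says "dose is unlikely to be available in Nordic data and sporadically available in US data". Appendix 3 rates US special-population dose adjustment as Partial (legend: "Partial = may be available for some patients") and US maintenance dose as Maybe. It shows neither as available in the four Nordic countries.

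**The concern.** A prescriber who lowers the dose because the label says so is following the label. Under (a)4 as worded, that patient is flagged for use inconsistent with it. Under the dose-adjustment objective, the same record counts towards the proportion aligned. The two results would contradict each other within one report.

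The flag also feeds a primary-objective percentage and the groups in which AESI incidence is compared. The patients concerned are by definition those with renal or hepatic impairment, and hepatotoxicity is one of the AESIs. Any misplacement would therefore not be random with respect to the outcomes.

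**Working it through.** **1. Reproduce the plan's dose.** The PASS Information table gives an 8 mg/90 mg tablet, and section 9.3.1.2 gives four tablets a day as standard.
4 × 8 mg = 32 mg and 4 × 90 mg = 360 mg. This matches the dose in (a)4.

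**2. Dose implied by the protocol's own allowance for impaired patients.** Section 9.3.1.1 gives 112 tablets per Nordic dispensing. Section 9.7.2 lets patients with renal or liver impairment take up to 56 days over each dispensing.
112 / 56 = 2 tablets a day; 2 × 8 mg = 16 mg and 2 × 90 mg = 180 mg.
That is half the standard dose. If a prescribed maintenance dose of 16 mg/180 mg were recorded, (a)4 would flag it. This figure is only what the 56-day allowance implies. The labels are not in the document, so it is not offered as the dose that any label directs.

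**3. One patient under each rule.** Take a US patient with moderate impairment, a recorded reduced dose that the label directs, and no other violation.

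| Rule | Result |
|---|---|
| Sections 8 and 9.7.2, criterion (a)4 | non-compliant |
| Section 8 dose-adjustment objective, section 9.7.4 | aligned |
| Section 9.7.2, 56-day sensitivity analysis | continued use and adherence recalculated; (a)4 flag unchanged |
| Section 9.7.2, reporting by component | counted under (a)4; overall split unchanged |

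**4. Who can be affected.**
- Nordic patients: dose is not expected to be recorded, and section 9.4.1 notes a single dose and pack type. The effect is essentially nil.
- US patients with no recorded dose: section 9.3.1.2 assigns the standard dose in primary analyses, so (a)4 is not triggered.
- End-stage renal failure and severe hepatic impairment: already non-compliant under (b)1 and (b)8, so only lesser impairment matters.
- What remains: US patients with a recorded, label-directed reduction and no other violation.

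**5. Conversion to size.** Section 9.4.2 anticipates more than 20,000 US users. Let *s* be the unknown share in the remaining group.
Patients moved = 20,000 × *s*; change in the non-compliant percentage = 100 × *s* points.
For *s* = 0.1%: 20,000 × 0.001 = 20 patients, 0.1 point.
For *s* = 1%: 20,000 × 0.01 = 200 patients, 1.0 point.
Both values of *s* are illustrations. The protocol gives no information on *s*.

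**The case against.** The best defence is that the SmPC is the governing standard and the list only illustrates it. Section 8 introduces the items as examples and says the compliance analysis will be adapted to the country's SmPC. Section 9.7.2 repeats the adaptation, and section 9.7.3.1 names the US for it. An analyst applying the US label in full, including any dose adjustment in it, might well not flag a label-directed dose. A US analysis plan, not shown, could also contain such a rule.

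Part of this stands. It makes misclassification a possibility, not an established result, and it lowers the weight of the point. It does not remove the conflict. The adaptation works by country and as needed, and says nothing about individual patients. An open-ended list of examples allows criteria to be added but does not exempt someone who meets a listed one. Section 8 marks severe hepatic impairment as dependent on the local SmPC but gives the dose item no such qualifier. The dose rule is stated, so this is a rule fixed badly and not a detail left open.

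It is also fair that reporting by component shows the (a)4 count. That count would not separate label-directed from off-label reductions.

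A reader might infer that the non-compliance percentage or the AESI comparison is materially distorted, perhaps in every country. The document does not support that. The affected group is a narrow intersection within one data source, where dose is recorded only sporadically, and the US label's own dosing instructions are not given.

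**Conclusion.** The point holds as a minor one. Criterion (a)4 is wrong as written because it fixes one dose for every patient, while the same protocol treats renal and hepatic dose adjustments as potentially aligned with the SmPC. The effect is limited to the US group identified above. Its size is unknown and probably small.

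The conclusion rests on a literal reading of (a)4 and on the US label directing a lower maintenance dose for some impaired patients who are not already contraindicated. The dose-adjustment objective and the 56-day analysis suggest that the authors expect such patients, but the document does not establish what the US label says.

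**What to change.** In sections 8 and 9.7.2, reword the item to: *a prescribed maintenance dose other than that specified by the applicable SmPC for that patient (32 mg/360 mg unless an SmPC dose adjustment for renal or hepatic impairment applies)*. Apply this to the US compliance flag and to the AESI subgroups built on it.

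No new data are needed: Appendix 2 already lists diagnosis codes for moderate or severe renal impairment (N18.3–N18.5) and hepatic impairment (K70, K72–K75). The cost is wording in two places and one classification rule in the US code. The Milestones table anticipated the US final report for August 4, 2023. If that report has been produced, the flag and its dependent tables must be re-tabulated for an effect that may prove small.
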